10.2.1 Subject Safety Monitoring

Subjects will be monitored throughout the study for the following:

- ALT or AST increase to $>5 \times$ Baseline
- ALT or AST increase $>2 \times$ Baseline AND the increase is accompanied by a concomitant Total Bilirubin increase to $>2 \times$ Baseline OR the INR (prothrombin time / partial thromboplastin time) concomitantly increases from Baseline by >0.2
- Elevated Baseline liver chemistry (AST or ALT elevations $2 \times$ Baseline) will require subjects to be reassessed promptly (within 48–72 hours) with full liver biochemistry and physical exam

- Elevations of ALT/AST accompanied by preferred terms indicating: signs or symptoms of right upper quadrant abdominal pain, anorexia, nausea, vomiting fever, eosinophilia, and/or rash

Incidence of these safety categories will be summarized by treatment group and identified on the listings with laboratory data parameters

10.3 Vital Signs

Vital signs will include heart rate (HR), respiratory rate (RR), blood pressure (BP) and oral temperature. Vital signs results will be summarized by timepoint where it shows change from Baseline, and significant changes in vital signs by treatment. Significant vital signs to be included are:

Pulse Rate

- < 50 bpm
- > 120 bpm
- ≥ 30 bpm increase from Baseline
- ≥ 30 bpm decrease from Baseline

Blood Pressure

- SBP > 150 mmHg or DBP > 100 mmHg
- SBP > 200 mmHg or DBP > 110 mmHg

Respiration Rate

- < 8 breaths/min
- > 40 breaths/min

Temperature

- > 38.3°C
- ≥ 1.1°C increase from Baseline (Baseline > 36.8°C)

Change in Weight

- ≥ 5% increase from Baseline
- ≥ 5% decrease from Baseline

All vital sign results will be listed.

Weight may be collected in kilograms (kg) or pounds (lb) and height may be collected in centimeters (cm) or inches (in). BMI will be reported in kg/m².

For metric measurements kg and cm:

$$\text{BMI} = \text{Weight}/[(\text{Height} \times 100)^2].$$

For English measurements lb and in:

$$\text{BMI} = [\text{Weight}/(\text{Height})^2] \times 703.$$

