### **8.2.3 Weight and Body Mass Index (BMI)**

Height should be recorded once at the Screening visit while weight should be recorded at the Screening and EOS visits. BMI should be calculated at the times shown in the SoA (Appendix 1) according to the following equation:  $BMI = \text{weight (kg)} / \text{height (m)}^2$ .

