8.1 Demographic and Baseline Characteristics

Baseline data will be summarized for continuous and categorical variables as applicable.

The following subject demographics and pre-dose values will be summarized in the Full Efficacy population:

- Age, and Age group (< 45 years, 45 to < 65 years, and \geq 65 years);
- PBC Diagnosis Age, and PBC Diagnosis Age group (<45, \geq 45)
(Age at diagnosis will be calculated as [year of diagnosis] minus [year of birth]. If only the subject's age at screening is available (rather than year of birth), then [year of signing consent (first consent)] minus [age at consent] will be used in place of [year of birth]);
- Duration of PBC, and Duration of PBC category (<7.5 years vs \geq 7.5 years);
- Sex, and Females of Child-Bearing Potential;
- Ethnicity, Race;
- Height, Weight, BMI;
- liver stiffness score;
- documented fibrosis stage;
- UDCA usage (Yes/No), UDCA Total Daily Dose (will be derived as the total daily dose recorded immediately prior to first dose of study drug - as an ongoing concomitant medication at that time; any changes in UDCA use are not expected and will not affect the derivation of this baseline characteristic);
- UDCA response status;
- ApoE Isoform (Genomics) as resulted at Day 1, if no Day 1 value is present reported as the next result available in the progression of study visits (i.e. Day 1, Week 2, Week 4, Week 8, Week 12, and EOS);
- Alkaline phosphatase (ALP): screening value, baseline (last pre-dose) value, average of all pre-dose values;
- Alanine Aminotransferase (ALT);
- Conjugated (direct), Unconjugated (indirect), and Total Bilirubin (unconjugated will be derived as total minus conjugated).
- Gamma-Glutamyl Transferase (GGT)

No statistical testing will be performed on the aforementioned demographic data.

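### The SAP's metric BMI formula multiplies height in centimetres by 100 instead of dividing, so BMI derived as written is too small by a factor of 10^8

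*SAP*

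**What the plan says.** SAP 10.3 (Vital Signs) allows weight in kilograms or pounds and says that "height may be collected in centimeters (cm) or inches (in"). Metres are not offered as a collection unit. It fixes the output unit: "BMI will be reported in kg/m²".

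Two derivation rules follow:

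- Under the lead-in "For metric measurements kg and cm", BMI is Weight/[(Height × 100)^2].
- For pounds and inches, BMI is [Weight/(Height)^2] × 703.

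Protocol 8.2.3 says that "BMI should be calculated at the times shown in the SoA (Appendix 1) according to the following equation" and then gives weight in kilograms divided by the square of height in metres.

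The derived variable is reported. SAP 8.1 lists "Height, Weight, BMI" among the characteristics to be summarised in the Full Efficacy population. SAP 11 also includes demographics in the reporting for the possible interim analysis.

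**The concern.** Centimetres become metres by dividing by 100. The SAP multiplies, so the conversion runs the wrong way and the error is then squared.

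This is an operative derivation rule that a programmer is meant to follow. The pounds-and-inches rule next to it is right, so records from the two unit systems would be on different scales within one table. The SAP lists the US and nine other countries as locations and provides for both unit systems, so both rules can be expected to be used.

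At stake is the accuracy of one row of the baseline table, and of any interim demographic output that carries BMI. No efficacy conclusion depends on it.

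**Working it through.** **Inputs**

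- Metric rule: Weight/[(Height × 100)^2], weight in kg and height in cm (SAP 10.3).
- Reporting unit: kg/m² (SAP 10.3).
- Pounds-and-inches rule: [Weight/(Height)^2] × 703 (SAP 10.3).
- Protocol definition: kg divided by metres squared (Protocol 8.2.3).
- The documents give no numerical BMI result to reproduce. The heights and weights below are assumed, for illustration only.

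**Step 1: general size of the error.** Let W be weight in kg and H height in cm.

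- Protocol definition: W/(H/100)^2 = 10^4 × W/H^2.
- SAP metric rule: W/(100 × H)^2 = 10^-4 × W/H^2.
- Ratio: 10^4/10^-4 = 10^8, whatever the height and weight.

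**Step 2: numerical check**

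| Weight, height | SAP metric rule | Protocol definition | Ratio |
|---|---|---|---|
| 50 kg, 150 cm | 50/15000^2 = 2.22 × 10^-7 | 50/1.50^2 = 22.22 | 10^8 |
| 70 kg, 165 cm | 70/16500^2 = 2.57 × 10^-7 | 70/1.65^2 = 25.71 | 10^8 |
| 70 kg, 170 cm | 70/17000^2 = 2.42 × 10^-7 | 70/1.70^2 = 24.22 | 10^8 |
| 100 kg, 185 cm | 100/18500^2 = 2.92 × 10^-7 | 100/1.85^2 = 29.22 | 10^8 |

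**Step 3: is the pounds-and-inches rule sound?** The exact constant is 0.45359237/0.0254^2 = 703.07, against the SAP's 703. For 70 kg and 170 cm converted to pounds and inches, the SAP rule gives 24.22, in agreement with the protocol. The fault is confined to the metric rule.

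**Step 4: does another reading rescue the metric rule?** If height were entered in metres, 70/(1.70 × 100)^2 = 0.00242, still wrong by 10^4. The SAP in any case says centimetres.

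**Step 5: effect on a pooled mean.** The documents do not give the share of metric records, so call it p. If everyone's true BMI were 24.22, the pooled mean under literal programming would be about (1 − p) × 24.22, because metric records contribute almost nothing:

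- p = 0.25: 0.75 × 24.22 = 18.2
- p = 0.50: 0.50 × 24.22 = 12.1
- p = 0.75: 0.25 × 24.22 = 6.1

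**The case against.** The strongest reply is that this is a typing slip that reveals itself. The SAP states the correct unit just before the formula, its Introduction says it is to be read together with the protocol, and the protocol's formula is right. Entry requires a Screening BMI of at least 18 kg/m², so a value near 2 × 10^-7 should be noticed at once. A wrong line in the SAP does not show that any BMI value was wrong. That stands: the error does harm only if the line is programmed literally and nobody looks at the output.

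The use of BMI is also limited, and this stands too. It is a descriptive baseline item without statistical testing. It is not among the ALP-response subgroups in SAP 9.1.2, and the ANCOVA models use treatment and the baseline value of the variable analysed. The weight-change thresholds in SAP 10.3 use weight, and eligibility is governed by the protocol.

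Two facts are unknown. The protocol has BMI calculated at the scheduled visits, and without the CRF one cannot tell whether a site-recorded BMI exists that the analysis might use instead. Nor do the documents say how many subjects are measured in metric units.

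Finally, the text was read from PDF by a program, so a misread operator cannot be ruled out. It seems unlikely: both BMI formulas write division with a slash, and a misread division sign would mean that the notation changed within one line.

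These points limit the consequence. None makes the formula correct, and no other SAP text corrects it.

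**Conclusion.** The metric rule in SAP 10.3 is wrong as written. It understates BMI by exactly 10^8 for every record in kilograms and centimetres and contradicts the SAP's own reporting unit, its pounds-and-inches rule and Protocol 8.2.3.

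The size of the error rests only on the units the SAP states, not on the illustrative subjects. Actual damage to the baseline table depends on two assumptions: that the rule is programmed literally, and that BMI is derived from it rather than taken from a site-recorded value. Priority is low, because no efficacy, safety or eligibility conclusion turns on it.

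**What to change.** Confirm the operator on the source page. Then replace the metric rule in SAP 10.3 with BMI = Weight/[(Height/100)^2], for weight in kg and height in cm. With that change, 70 kg and 170 cm gives 70/1.70^2 = 24.22 kg/m², matching the protocol and the pounds-and-inches rule.

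The cost is one operator. The SAP already provides the route, through its change log and a final amended version before database lock. If lock has passed, the sponsor should confirm which formula was programmed and record the correction in the clinical study report. A range check on derived BMI would catch any remaining unit error; the Screening minimum of 18 kg/m² gives a ready lower bound for baseline values.

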10.4 Physical Exam Data

All physical exam results will be listed along with descriptions of any abnormality.

10.5 ECG Results

ECG results including PR, QRS, QT, RR, and QTc (QTcF) intervals will be summarized by timepoint where it shows change from Baseline with a summary for defined thresholds:

QTcF Maximum value

- ≤ 450 msec
- > 450 to ≤ 480
- > 480 to ≤ 500 msec
- > 500 msec

QTcF Maximum change from Baseline

- ≤ 30 msec
- > 30 to ≤ 60 msec
- > 60 msec

Females with Screening or Baseline < 470 msec
Males with Screening or Baseline < 450 msec

ECG results will be listed for all timepoints and clinically significant results will be flagged. The ECG parameter, QT interval (msec) will be adjusted for the length of the RR interval (msec) using the Fridericia correction (QT interval length divided by cube root of the interval from the onset of one QRS complex to the next) as follows:

$$QTcF = QT / \text{cube root}(RR).$$

RR will be converted to seconds for the calculation.

11 Interim Analyses

An administrative interim analysis may be conducted after approximately 25% of the planned total number of subjects (~30 subjects) have been enrolled and completed 12 weeks of treatment.

No study stopping rules have been established and no inferential testing will be performed.

Reporting for interim analysis will include the subject disposition, demographics, the primary endpoint, and secondary efficacy variables. See Appendix 4 for the list of outputs.

Results of the interim analysis will remain blinded to all blinded team members at Enanta and PRA. PRA will create the reporting with blinded treatment codes, and an unblinded PRA team will merge the data with the actual treatment codes for delivery of the unblinded interim analysis to the appropriate members of the Enanta management.

12 Data Safety Monitoring Board

The DSMB will meet on a periodic basis to review safety data. Refer to the DSMB charter for this study for information on the content and conduct for these meetings. Data review meetings will occur after groups of 20 subjects have completed 4 weeks of study drug treatment. The DSMB will receive fully unblinded results. The same team described in the above section will be responsible for providing unblinded outputs to the DSMB independent, unblinded statistician who will distribute the results to the DSMB members.

See Appendix 4 for the list of outputs.

13 References

Appendix 1 Glossary of Abbreviations

Glossary of Abbreviations:	
AE	Adverse event
ALP	Alkaline Phosphatase
ALT	Alanine Aminotransferase
ANCOVA	Analysis of Covariance
APRI	AST to Platelet Ratio Index
AST	Aspartate Aminotransferase
ATC	Anatomic Therapeutic Classification
AUC _{last}	Area Under the Concentration-time curve at last measurement
BP	Blood Pressure
C _{max}	Maximum concentration
CMH	Cochran-Mantel-Haenszel (test to compare proportions)
CRF	Case Report Form
CSR	Clinical Study Report
CTMS	Clinical Study Management System
CYP450, CYP3A4	Cytochrome P450, Cytochrome P450 3A4
CYP7A1	Cholesterol 7 α -hydroxylase
DMC	Data Monitoring Committee
DSMB	Data Safety Monitoring Board
ECG	Electrocardiogram
EDC	Electronic Data Capture
EOT	End of Treatment
FIB-4	Fibrosis 4 Index
GGT	Gamma-Glutamyl Transferase
HP	High Panic Laboratory test value indicating “potentially critical implications”
HR	Heart Rate
HT	High Telefacsimile Laboratory test value indicating “warrants notification”
IVRS	Interactive Voice Response System
LLN	Lower Limit of Normal
LP	Low Panic Laboratory test value indicating “potentially critical implications”
LT	Low Telefacsimile Laboratory test value indicating “warrants notification”
PBC	Primary Biliary Cholangitis
PD	Pharmacodynamics

PBO	Placebo
P-gp	p-glycoprotein
PK	Pharmacokinetics
PP	Per Protocol
QoL	Quality of Life
QTcF	QT interval, Fridericia correction
SAP	Statistical Analysis Plan
SAE	Serious Adverse Event
SD	Standard Deviation
TEAE	Treatment Emergent Adverse Event
TFL	Table, Figure and Listing
T _{max}	time to maximum concentration
UDCA	Ursodeoxycholic Acid
ULN	Upper Limit of Normal
VAS	Visual Analog Score
WHODRUG	World Health Organization Drug Dictionary

Appendix 2 Adverse Event Start/Stop Date Imputation

Imputation Rules for Partial Dates (D = day, M = month, Y = year)

Parameter	Missing	Additional Conditions	Imputation
Start date for AEs	D	M and Y same as M and Y of first dose of study drug	Date of first dose of study drug
		M and/or Y not same as date of first dose of study drug	First day of month
	D and M	Y same as Y of first dose of study drug	Date of first dose of study drug
		Y prior to Y of first dose of study drug but same as Y of screening date	Date of screening date
	D, M, Y	None - date completely missing	Date of first dose of study drug
Stop date for AEs	D	M and Y same as M and Y of last dose of study drug	Date of last dose of study drug
		M and/or Y not same as date of last dose of study drug	Use last day of month
	D and M	Y same as Y of last dose of study drug	Date of last dose of study drug
		Y not same as Y of last dose of study drug	Use Dec 31
	D, M, Y	None - date completely missing	No imputation, but assume ongoing

Note: In all cases, if an estimated start date is after a complete stop date, use the first day of the stop date month.

Similarly, if the estimated stop date is before a complete or imputed start date, use the last day of the start day month.

Appendix 3 Prior and Concomitant Medication Start/Stop Date Imputation

Imputation Rules for Partial Dates (D = day, M = month, Y = year)

Parameter	Missing	Additional Conditions	Imputation
Start date for con meds	D only	M and Y same as M and Y of first dose of study drug	Date of first dose of study drug
		M and/or Y not same as date of first dose of study drug	First day of month
	M and D	Y same as Y of first dose of study drug	Date of first dose of study drug
		Y not same as Y of first dose of study drug	Use Jan 01 of Y
	M, D, and Y	None - date completely missing	Day prior to date of first dose of study drug
	Stop date for con meds	D only	M and Y same as M and Y of last dose of study drug
M and/or Y not same as date of last dose of study drug			Last day of month
M and D		Y same as Y of last dose of study drug	Date of last dose of study drug
		Y not same as Y of last dose of study drug	Use Dec 31 of Y
M, D, and Y		None - date completely missing and NOT ongoing	Date of last dose of study drug

Note: In all cases, if an estimated start date is after a complete stop date, use the first day of the stop date month.

Similarly, if the estimated stop date is before a complete or imputed start date, use the last day of the start day month.

Appendix 5 Schedule of Assessments (SoA)

Study Event	Scr. ¹ (D-28 to -1)	Study Assessments per Planned Study Day						EOS	
		D1 ²	D3	D14±2 W2	D28±2 W4	D56±2 W8	D84 ³ ±2 EOT ⁵ /W12	D112±2 W16	
ICF ⁶ ; Demography; Medical History	X								
Inclusion/Exclusion	X								
FSH ⁷ ; HIV/HCV/HBV	X								
AMA/M2/PBC-ANAb ⁸	X								
Pregnancy Test ⁹	X	X			X	X	X	X	
Height ¹⁰ , Weight, BMI	X							X	
PT/PTT and INR	X							X	
Oral Temperature	X	X						X	
Physical Exam ¹¹	X	X	X	X	X	X	X	X	
Vital Signs ¹²	X	X	X	X	X	X	X	X	
ECG	X	X	X		X		X		
Safety Lab. Tests ¹³	X	X	X	X	X	X	X	X	
PBC-40 QoL		X			X	X	X	X	
VAS and 5-D Itch		X			X	X	X	X	
Biomarkers (FGF19, C4, BA) ¹⁴		X		X	X	X	X		
CV Markers ¹⁵		X		X	X	X	X	X	
Fibroscan	X								
ELF panel, PRO-C3, Inflammatory Markers ¹⁶	X	X					X		
APRI, FIB-4		X					X		
PK/PD Substudy (PK, C4, FGF19, BA, ALP) ¹⁷		X		X	X	X	X		
Population PK Samples ¹⁸		X		X	X	X	X		
Dispense Study Drug		X			X	X			
Study Drug Dosing ¹⁹				daily dosing					
Drug Accountability			X	X	X	X	X		
AEs & Con Meds ²⁰	X	X	X	X	X	X	X	X	

- 1 Screening assessments should be conducted within 28 days prior to the first dose of study drug (i.e., Study Days -28 to -1)
- 2 On Day 1, all samples are to be collected predose with the exception of respective post-dose PK and PD samples
- 3 Subjects should discontinue drug on Day 84. Subjects who return for their EOT Visit after Day 84, should stop dosing on Day 84.
- 4 For the treatment phase, indicates number of completed weeks of treatment
- 5 Subjects who discontinue treatment early should complete the EOT procedures as soon as possible and return 4 weeks later for the EOS visit
- 6 Informed consent must be obtained prior to conducting any study-specific procedures or assessments
- 7 For post-menopausal women only
- 8 Only if historical values are not available; one test must be positive for study entry to confirm PBC diagnosis (see Inclusion Criterion #3)
- 9 Serum pregnancy test at Screening and Baseline, and urine pregnancy testing at Baseline and all other visits. If the urine pregnancy test is positive, a serum pregnancy test should be obtained as soon as possible to confirm.
- 10 Height should only be measured at Screening
- 11 Full PE at Screening and EOS; all other exams should be targeted to review of new signs and symptoms
- 12 Vital Signs include HR, respiratory rate, and BP and will be measured once in the morning before the morning dose of study drug
- 13 Safety laboratory tests include chemistry (including liver function tests), hematology, and urinalysis and should be collected predose at all visits; See Section [12.6.3.2](#) for details

14 Biomarkers include fasting plasma FGF19, fasting serum bile acids, fasting C4 (7 α -OH-4-cholesten-3-one). Samples should be collected after a minimum 8 hr fast and before the subject takes the daily dose of study drug

15 Lipids and CV risk markers to be collected are detailed in Section [12.6.3.2](#)

16 Markers of inflammation include fibrinogen, CRP, IL6, IL1 β , TNF- α , TNF- β , alpha2 macroglobulin and haptoglobin see Section [12.6.3.2](#)

17 Collect PK/PD samples after a minimum 8 hr fast and before the daily dose of study drug. PK/PD samples on Days 1 and 84 (Week 12) collected predose and 2, 6, and 8 hr postdose; Weeks 2, 4 and 8 at predose and two samples postdose; the first sample collected 1 to 3 hours postdose and the second sample at least 1 hour later.

18 PK predose samples should be collected after a minimum 8 hr fast before the daily dose of study drug. PK samples collected Day 1, Weeks 2, 4, 8 and 12 at predose and two samples postdose; the first sample collected 1 to 3 hours postdose and the second sample at least 1 hour later.

19 Study drug given in the clinic on days where subject is seen in the clinic

20 Additional samples may be collected to further assess safety events e.g. pruritus

■ [REDACTED]

Appendix 6 Laboratory Evaluations

Chemistry Panel
 
 • Alanine Aminotransferase (ALT/SGPT) • Albumin, Serum • Albumin/Globulin (A/G) Ratio (calculation) • Alkaline Phosphatase, Serum • Amylase • Aspartate Aminotransferase (AST/SGOT) • Bilirubin, Total and Direct • BUN • BUN/Creatinine Ratio (calculation) • Calcium, (Serum) • Creatine Kinase • Creatinine, Serum (creatinine clearance) • Uric Acid • Electrolyte Panel (Na+, K+, Cl-, Bicarb.) • Phosphorus • Gamma Glutamyl Transferase (GGT) • Globulin, Total • Glucose, Serum • Cholesterol, serum • Lactate Dehydrogenase (LDH) • Lipase • Protein, Total, Serum • TG (triglycerides) • HDL Cholesterol 1 • LDL Cholesterol 1 • Apolipoprotein E (ApoE) 	
Hematology Panel
 
 • Hemoglobin • Hematocrit • Differential WBC Count (percentage and absolute): Basophils, Eosinophils, Lymphocytes, Monocytes, Neutrophils • MCH • MCHC • MCV • Platelets • Red Blood Count • RBC Morphology • White Blood Count • Absolute Neutrophil count)

Coagulation
 
 • INR • PT • PTT 	
Urinalysis Panel
 
 • Color and appearance • PH • SG • Bilirubin • Glucose • Ketones • Leukocytes • Nitrite • Occult blood • Protein • Urobilinogen • Microscopic (including RBCs and WBCs) • Bacteria • Leukocyte Esterase 
Safety Monitoring
 
 • Liver Enzymes 
 ○ Total Bilirubin, Direct Bilirubin, Alkaline Phosphatase, ALT(SGPT), AST(SGOT), GGT • Liver Hematology 
 ○ RBC, Neutrophils(abs, %), Lymphocytes(abs, %), Monocytes(abs, %), Eosinophils(abs,%), Basophils(abs,%), Platelets • Elevated Liver Coagulation 
 ○ INR, PT • Albumin

Appendix 7 Markers of CV Risks and Lipids and Markers of Fibrosis and Inflammation

Markers of CV Risks and Lipids	Markers of Fibrosis and Inflammation

 • hs-CRP • HDL-P • LDL-P • apoA-I • apoB • apoB/A Ratio • apoC3 • apoE isoforms (E2, E3, E4) • Total Cholesterol (TC) • High Density Lipoprotein – Cholesterol (HDL-C) • Low-Density-Lipoprotein – Cholesterol (LDL-C) • TG (triglycerides) • Total /HDL Cholesterol (CT) Ratio • Adiponectin 	
 • Enhanced Liver Fibrosis (ELF) Panel 
 ○ Hyaluronic acid (HA), ○ Procollagen III amino terminal peptide (PIIINP) ○ Tissue inhibitor of metalloproteinase 1 (TIMP-1) • PRO-C3 • Fibrinogen • CRP • alpha2 macroglobulin • haptoglobin • TNF-α • TNF-β • IL-6 • IL1β • AST to Platelet Ratio Index (APRI) • Fibrosis 4 (FIB-4) Index

Statistical Analysis Plan

Sponsor:	Enanta Pharmaceuticals, Inc.
Protocol No:	EDP 305-201
PRA Project Id:	ENA30501-30501
Version Date:	09-MAR-2020
Version No.:	7.0

Title:	A Phase 2 Dose Ranging, Randomized, Double Blind, Placebo-Controlled Study Evaluating the Safety, Tolerability, Pharmacokinetics and Efficacy of EDP-305 in Subjects with Primary Biliary Cholangitis (PBC) with or without an Inadequate Response to Ursodeoxycholic Acid (UDCA)
CRF Version No./Date:	3.0/01-Aug-2018
SAP No.	1.4
